Group 2 (or experimental EmoLED protocol group) will be visited once a week. Therapy in this case includes, in addition to the standard therapy, a treatment with EmoLED device; it consists in irradiating each 5 cm diameter area of the lesion for 60 seconds, with the blue light emitted by the device. For lesions larger than 5 cm, several applications will be applied on adjacent areas, until the whole lesion is covered.

EmoLED is a medical device for light therapy (Class IIa), portable and battery-powered. Its intended use is the care of acute and chronic skin lesions by healthcare staff on patients over 16 years old, regardless of their ethnicity. Related adverse events, incidents or side effects haven't been observed during previous clinical trials and clinical experiences; therefore, no risks are reported in addition to the ones related to the use of light in medicine. However, the device is labelled and written instructions are provided for a safe use.

The objective of the study is to assess eventual differences in the outcome between the two groups and to determine if the therapy of Group 2 is a valid alternative to the standard therapy in terms of healing rate, quality of life and economic impact:

- The primary endpoint of the study is the percentage/rate of lesion area reduction
- The secondary endpoints are, together with other clinical parameters aimed at evaluating the general clinical situation, quality of life and costs related to the two treatments.

There is a follow-up after 4 weeks since the end of the period of observation (it may end at the 16th week or earlier).

Ethical considerations

The study will be submitted to the Ethical Committee of each investigator hospital for approval and in any case will be performed according to the GCP, the Helsinki Declaration and the Italian laws and requirements in the matter of human clinical trials.

L.U.C.E. Study Protocol version 3.0 (24/02/2020)

10

Informed consent procedure

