As further detailed in the section on statistical analysis, it is expected to register, during the time of observation, a difference in efficacy between EmoLED protocol group ("Group 2") and SOC protocol group ("Group 1"), in terms of "healing rate", intended as a reduction of the wound area, but also as a progress, in a broad sense, of the overall clinical situation of the lesion, in terms of pain and quality of life.

Endpoint

Primary endpoint of the study

The primary endpoint will be the outcomes comparison in terms of healing rate of lesions treated with SOC only versus lesions treated with EmoLED and SOC, on week 16th.

L.U.C.E. Study Protocol version 3.0 (24/02/2020)

Secondary endpoint

- 1) Safety of treatment
- 2) Evaluation of the healing time of the lesions treated with the standard method (Group 1) versus the lesions treated with the EmoLED Protocol (group 2);
- Evaluation of the treatment of chronic ulcers in patients undergoing standard treatment versus EmoLED treatment about life quality (QoL) in 16 weeks, through generic questionnaires as the EuroQiL-5D2 and specific questionnaires as the Wound-Qol3;
- 4) Evaluation of costs related to the treatment and control group, in both the NHS and society perspective
- 5) Evaluation of VAS scale in both groups;
- 6) Evaluation of satisfaction, complexity and helpfulness of EmoLED device, considering both the perspective of patients, and the one of doctors and health care workers involved;
- 7) Evaluation of cost-effectiveness using EmoLED for the treatment of ulcers.

Measurable parameters

The key data and lesion's pictures of each patient will be collected in the Data Collection Form, after the enrollment and the signature of the Informed Consent:

- Group 1: V1 (Visit 1 and first treatment), V2, V3, V4... until V32 (32 treatments are planned during 16 weeks, 2 per week)
- Group 2: V1 (Visit 1 and first treatment), V2, V3, V4... until V16 (16 treatments are planned during 16 weeks, 1 per week)

The parameters used to define the study result will be found through:

- Photographic images of lesions treated with EmoLED and control lesions
- Data Collection Form filled by the medical staff during the visit
- Economic/organizational impact survey
- Medical/clinical/social impact survey
- Survey on the usability of the device
- Detection of pain through VAS scale

Registration of clinical data

The data related to the evaluation of the study endpoints are acquired, for both groups, during the visits.

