The parameters of the Data Collection Form are acquired and kept on paper for the clinical trial lenght, and conserved in both paper and digital form; the pictures of the lesion are acquired and kept in digital form, during the length of the clinical trial and afterwards.

During each visit, a picture of the lesion will be taken so that the process of healing can be valued also in a visual way. Each picture will be named with the patient code and the date of the visit. In case of multiple lesions matching with both inclusion and exclusion criteria, they will be all treated following the same protocol, depending on the group of treatment, but only the lesion with the wider area will be registered; to distinguish the area of interest, the perilesional tissue will be labelled with single-use permanent markers.

Data Collection Form

The Data Collection Form is unique for each patient and includes: Clinical Section, Quality Life Section and Economic Section. The Clinical Section contains identification code of the patient, date of birth, sex, etiology of the ulcer, any eventual concurrent disease, any drug therapy (in terms of active substances), ulcer's date of onset, date of entry to the facility.

The second part of the form is organized as a matrix where the row represents the measurable parameters for each time of observation (reported in column).

The investigator marks with an "X" the chosen value for each parameter and the most suitable description. The Principal Investigator will also fill a check list, for each visit, to ensure that also the pain level has been measured and that the picture of the lesion has been taken.

There is also a "Notes" section to register information not planned at first, that might be helpful during the data analysis.

The last part of the Data Collection Form is about follow-up visit (after 4 weeks).

The Data Collection Form is already completed with the patient's recruitment code and the group they belong to, so that the allocation to the EmoLED group and the control group is random. The allocation sequence of the group is generated by Matlab.

On each visit, the patient will be asked to rate their current pain level (VAS scale 0-10).

The quality section survey will be administered on the first and last visits, and also every 4 weeks. In detail, standard questionnaires as the EQ-5D2 and the Wound-Qol3 will be administered, both available and validated in Italian language.

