80 patients will be recruited during the study; they will be randomized 1:1 to the standard treatment group and the EmoLED Protocol group. In the control group, which follows the standard treatment, patients will be visited twice a week. The EmoLED experimental Protocol group will undergo medical examination once a week; in this case, therapy will consist in the standard treatment plus EmoLED treatment.

This sample size is sufficient to compare the average rate of the injured area reduction, considering Student-T test for the comparison between independent samples, by establishing $\alpha = 0.05$, power level (1- β) = 0,8, under the assumption to have an area reduction rate after 16 weeks amounting to 50% in Group 1 (control group), a difference of 20% between Group 2 (experimental group) and Group 1, a standard deviation of averages equal to 50% of the mean values and a bilateral hypothesis.

Statistical analysis

The average rate of reduction of the injured area between the two groups will be compared using the Student-T-test, the quality of life in both groups at the baseline, after 16 weeks and the difference with the baseline will be compared using Student-T-test for independent samples.

Linear regression models will be used to value the differences between the groups to exclude any confounding factors. Due to the usually asymmetrical nature of cost distribution, the comparison of the costs related to the treatment and control group, in both the NHS and society perspective, will be made using the non-parametric Mann-Whitney U test.

Generalized linear regression models will be used to value the differences between the groups to eliminate any confounding factors.

The cost-effectiveness of both treatments in the time frame of the study (16 weeks) will be valued by calculating the incremental cost-effectiveness ratio (ICER) and expressed in terms of incremental costs for "quality adjusted years (QALY).

Extrapolations of results about the cost-effectiveness that simulate longer time-frames will be made considering decision-making models (e.g. Markov models) and eventually including the data gathered during the study with literary data and/or evidence from other studies.

Data publication policy

L.U.C.E. Study Protocol version 3.0 (24/02/2020)

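### Quality of life is compared by unadjusted t-tests at baseline, at week 16 and on change, with none designated as the treatment comparison; one week-16 comparison adjusted for baseline would settle this at almost no cost

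*Combined protocol and SAP*

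**What the plan says.** The section Statistical analysis states that "the quality of life in both groups at the baseline, after 16 weeks and the difference with the baseline will be compared using Student-T-test", in the form for independent samples. None of the three comparisons is named as the one that estimates the effect of treatment.

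The section Secondary endpoint has QoL assessed "through generic questionnaires as the EuroQiL-5D2 and specific questionnaires as the Wound-Qol3". The three comparisons therefore presumably apply to each of two questionnaires. The section Data Collection Form gives the timing: "The quality section survey will be administered on the first and last visits, and also every 4 weeks". A baseline score and intermediate scores are thus already part of the data.

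Directly after the t-tests for area and QoL, Statistical analysis adds: "Linear regression models will be used to value the differences between the groups to exclude any confounding factors". It names no covariate and does not say whether the regression or the t-tests carry the conclusion.

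Two sections bear on how the baseline score is obtained. Data Collection Form describes one form per patient that contains the QoL section and already shows the patient's group. Bias explains that these forms come in sealed folders, with the group label inside.

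**The concern.** A randomised comparison of QoL needs one stated estimate of the treatment effect. The plan offers two, week 16 and change from baseline, and adds a baseline test that is not a treatment comparison at all. If the two disagree, nothing in the plan says which is the QoL result, so the choice can be made after the data are seen.

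Precision is also at stake. The baseline scores are collected in any case, yet the week-16 test ignores them and the change test uses them with a fixed weight that is generally not the best one. QoL is one of the grounds, with healing rate and economic impact, on which Objectives of the study wants to judge whether the experimental schedule is a valid alternative. It is therefore worth knowing beforehand which number will speak for it.

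**Working it through.** **Inputs from the documents.** Under Calculation of the sample size, the plan says that "80 patients will be recruited during the study; they will be randomized 1:1 to the standard treatment group and the EmoLED Protocol group"; Number of patients expected to enroll gives 40 per arm. The plan states no SD, correlation, target difference or power for QoL, so it has no QoL figure to reproduce. Its sample-size statement concerns area reduction only. Read as 50% against 70% with SDs of 25 and 35, the pooled SD is sqrt((25² + 35²)/2) = 30.4, and the t-test needs 38 per arm for 80% power. On that reading 40 per arm is sufficient, as stated. The QoL point does not depend on it.

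**Assumptions.** Complete, roughly normal scores in 40 per arm; equal SDs at baseline and week 16 (set to 1); correlation ρ between baseline and week 16 of 0.3, 0.5 or 0.7; where power is shown, a true effect of 0.5 SD.

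**Step 1: the gap between the two estimates.** In the same patients,

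(week-16 difference) − (difference in change) = baseline difference.

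This is an identity. If the baseline difference is chance, its standard error is sqrt(2/40) = 0.224 SD, whatever ρ is. Its median absolute size is 0.6745 × 0.224 = 0.151 SD, and it exceeds 0.30 SD in 18% of trials.

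**Step 2: efficiency.** All three estimates have the form (week-16 difference) − b × (baseline difference), with variance (2/40)(1 − 2bρ + b²).
- Week-16 test: b = 0, factor 1.
- Change test: b = 1, factor 2(1 − ρ).
- Baseline-adjusted comparison (ANCOVA): b estimated, aiming at the minimum b = ρ, factor 1 − ρ².

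Patients needed relative to ANCOVA are therefore 1/(1 − ρ²) for week 16 and 2(1 − ρ)/(1 − ρ²) = 2/(1 + ρ) for change.

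| Assumed ρ | 0.3 | 0.5 | 0.7 |
|---|---|---|---|
| Week 16, relative size | 1/0.91 = 1.10 | 1/0.75 = 1.33 | 1/0.51 = 1.96 |
| Change, relative size | 2/1.3 = 1.54 | 2/1.5 = 1.33 | 2/1.7 = 1.18 |
| Power at 0.5 SD, week 16 | 60% | 60% | 60% |
| Power at 0.5 SD, change | 47% | 60% | 82% |
| Power at 0.5 SD, ANCOVA | 64% | 72% | 87% |

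The power rows are simulated with t critical values. The simulated type I error of ANCOVA stayed at about 5%.

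**Step 3: how often the two tests part.** The correlation between the two test statistics is (1 − ρ)/sqrt(2(1 − ρ)) = sqrt((1 − ρ)/2) = 0.59, 0.50 and 0.39. With a 0.5 SD effect, one of the two is significant at 5% and the other not in about 32%, 32% and 35% of trials (bivariate normal). For effects from 0.3 to 0.7 SD the range is 12% to 40%.

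**Step 4: the condition on the baseline score.** Treating the baseline difference as chance requires the questionnaire to be answered before the arm is known. Suppose knowledge of the arm shifted baseline answers by 0.2 SD (an assumption). The bias through this route would be 0 for the week-16 test, 0.20 SD for the change test, and ρ × 0.2 = 0.06, 0.10 or 0.14 SD for ANCOVA.

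**The case against.** **Adjustment is probably already planned.** The linear-regression sentence follows the area and QoL t-tests and comes before the cost analysis, which has its own sentence on generalized linear models. The natural reading is that linear regression covers area and QoL. This stands. A reader might infer that no adjusted QoL analysis is foreseen, and the text does not support that. What is missing is the covariate and the role: baseline QoL is not named, and the plan does not say whether the model or the t-tests lead.

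**Adjustment is not free without a condition.** As described, the baseline questionnaire sits in a form and folder that show the group. This also stands, and Step 4 shows its effect. The documents do not show that any patient answers after learning the arm, so contamination of the baseline should not be inferred. The order of events simply needs to be stated.

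**Only two tests compete.** Correct: the baseline test is superfluous, but it is not a third treatment estimate.

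**The figures are hypothetical.** The correlations and effect sizes are assumed. Differing verdicts means one p-value below 0.05 and the other above it, not opposite conclusions. The identity in Step 1 and the absence of a designated comparison need none of these assumptions.

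**A multiplicity reading is tempting.** With no true effect, at least one of the two post-baseline tests is significant in 8.8%, 9.1% and 9.4% of trials per questionnaire, and in 14.5% to 17.8% across both. A reader might infer an inflated error rate. That follows only if any significant test counts as success, and the plan states no such rule.

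**Conclusion.** The point holds as a gap in specification with a better method readily available. The plan does not identify the QoL treatment comparison. The two candidates differ by the baseline difference (standard error 0.224 SD with 40 per arm if it is chance), and neither is more efficient than baseline adjustment. How much is lost depends on a correlation that the documents do not give: between 1.10 and 1.96 times the patients for week 16, and between 1.18 and 1.54 times for change, over ρ from 0.3 to 0.7 with equal SDs and complete scores.

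A reader might also infer that the t-tests are invalid or that the main result is at risk. Neither follows. With a baseline taken before allocation is known, each post-baseline t-test is a valid test in a randomised trial. QoL is secondary. For area reduction, the t-test is implicitly the primary analysis: the trial is sized on it ("This sample size is sufficient to compare the average rate of the injured area reduction, considering Student-T test for the comparison between independent samples") and Statistical analysis lists it first ("The average rate of reduction of the injured area between the two groups will be compared using the Student-T-test"). No change to that test is called for.

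**What to change.** In Statistical analysis:
- For each questionnaire, designate one week-16 between-group comparison adjusted for baseline QoL as the QoL treatment comparison. This can be ANCOVA, that is, the linear regression already planned with baseline QoL named as covariate, or a repeated-measures model that also uses the 4-weekly scores. With complete scores the two are about equally precise at week 16; the second also uses the interim scores of patients without a week-16 score.
- Report baseline QoL by group descriptively, without a test.

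In Data Collection Form or Bias: state that the baseline questionnaire is completed before the allocation is seen. Because the form and folder carry the group, this may mean handing out that questionnaire separately.

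Optional clarifications: name a lead questionnaire, or say that both are reported without a claim of success; say how patients whose observation ends early enter the analysis, since the follow-up wording in Objectives of the study is that "it may end at the 16th week or earlier" and a last-visit score is then not a week-16 score; and add one sentence calling the area t-test primary and listing the regression covariates.

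Cost: a few sentences, one instruction to sites and one degree of freedom. No extra patients, visits or questionnaires are needed.

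### Quality of life is collected every 4 weeks, but the stated between-group comparison uses only baseline, week 16 and the change, leaving weeks 4, 8 and 12 out

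*Combined protocol and SAP*

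**What the plan says.** Collection (Data Collection Form section): "The quality section survey will be administered on the first and last visits, and also every 4 weeks". The instruments are named there too: "standard questionnaires as the EQ-5D2 and the Wound-Qol3 will be administered". With 16 weeks of observation this gives weeks 0, 4, 8, 12 and 16.

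Endpoint (Secondary endpoint section, third item): the comparison is of "standard treatment versus EmoLED treatment about life quality (QoL) in 16 weeks". No single time point or summary measure is named.

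Analysis (Statistical analysis section): "the quality of life in both groups at the baseline, after 16 weeks and the difference with the baseline will be compared", and the method is that these "will be compared using Student-T-test for independent samples".

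Two other sentences in that section could touch the interim readings:
- The regression sentence, "Linear regression models will be used to value the differences between the groups to exclude any confounding factors", names no outcome, covariate or time point.
- The cost-effectiveness of both treatments over 16 weeks "will be valued by calculating the incremental cost-effectiveness ratio (ICER) and expressed in terms of incremental costs for" QALYs. The plan does not say which EQ-5D assessments build them.

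The Objectives of the study section adds that a patient's observation period may finish before week 16.

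**The concern.** Three of the four post-baseline readings of each questionnaire are collected from patients and then given no place in the comparison that answers the quality-of-life endpoint.

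This matters because of how the protocol expects the device to help. The rationale describes the potential benefit as a shorter healing time, and healing time is itself a secondary endpoint. If one arm heals sooner and the other catches up, the quality-of-life difference lies mainly in the middle of the observation period and may have narrowed by week 16. That is an inference from the protocol's rationale; the protocol does not state it.

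Two further consequences follow. A patient who answered at weeks 4 to 12 but not at week 16 contributes nothing to the week-16 or change comparison. And if the interim readings are analysed later without a prior statement, that analysis will be post hoc.

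**Working it through.** **Schedule against analysis**

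| Week | Collected | In the stated comparison |
|---|---|---|
| 0 | yes | yes (baseline, and in the change) |
| 4 | yes | no |
| 8 | yes | no |
| 12 | yes | no |
| 16 | yes | yes (value and change) |

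Five occasions are collected, two are used and three are not. The plan gives no quality-of-life effect, SD, correlation or power, so there is no figure of its own to reproduce.

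**Illustration of size**

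From the plan: 40 per arm, two-sided 5%. Assumed: SD 1 at each visit, one common correlation ρ = 0.6 between all visits, no loss, and the two effect patterns below. Power is Φ(d/SE − 1.96), with SE = √(2v/40) and v the per-patient variance:

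- Week-16 t-test: v = 1, SE = 0.2236.
- Change t-test: v = 2(1 − ρ) = 0.80, SE = 0.2000.
- Baseline-adjusted week 16: v = 1 − ρ² = 0.64, SE = 0.1789.
- Baseline-adjusted average of weeks 4-16: v = (1 + 3ρ)/4 − ρ² = 0.70 − 0.36 = 0.34, SE = 0.1304.

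The early pattern has effects of 0.2, 0.5, 0.5 and 0.3 SD at weeks 4, 8, 12 and 16 (mean 0.375). The late pattern has 0.1, 0.2, 0.3 and 0.5 SD (mean 0.275).

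| Analysis | Early: d/SE | Power | Late: d/SE | Power |
|---|---|---|---|---|
| Week-16 t-test (planned) | 0.3/0.2236 = 1.34 | 27% | 0.5/0.2236 = 2.24 | 61% |
| Change t-test (planned) | 0.3/0.2000 = 1.50 | 32% | 0.5/0.2000 = 2.50 | 71% |
| Baseline-adjusted week 16 | 0.3/0.1789 = 1.68 | 39% | 0.5/0.1789 = 2.80 | 80% |
| Baseline-adjusted average | 0.375/0.1304 = 2.88 | 82% | 0.275/0.1304 = 2.11 | 56% |

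The steps down to the third row come from the use made of baseline, which is a separate matter. Only the last step, 39% to 82% or 80% to 56%, comes from bringing in the interim visits.

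**Variance, average against baseline-adjusted week 16, no loss.** For ρ = 0.5, 0.6 and 0.7 the ratios are 0.375/0.75 = 0.50, 0.34/0.64 = 0.53 and 0.285/0.51 = 0.56.

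**Variance, same week-16 question.** With no loss, the interim readings add nothing to the week-16 contrast. With 20% loss spread evenly over the last three intervals, generalised least squares on all readings has 0.97, 0.96 and 0.95 of the variance of the baseline-adjusted completers' comparison for ρ = 0.5, 0.6 and 0.7. With a serial correlation of 0.9 it has 0.91. The like-for-like gain is therefore about 3-5%, and up to 9%.

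**The case against.** Four objections carry weight.

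- **Week 16 is a defensible choice.** It matches the primary endpoint's time point. The large power difference arises because the average over weeks 4-16 is a different quantity, under assumed effects, and the late pattern reverses the ranking. This stands. A reader might infer that the average is simply the better analysis, or that the plan wastes about half its information; neither is supported. For week 16 itself the gain is small.

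- **The interim data may already have a use.** A reader might infer that they are used nowhere in the plan. For EQ-5D that goes too far: a QALY over 16 weeks is a natural use of repeated utilities, and the regression sentence excludes no time point. But neither sentence assigns these readings to the between-group comparison, and the plan gives Wound-QoL no part in the QALY.

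- **Early end of observation.** A tempting illustration is an ulcer that heals at week 6 in one arm and week 14 in the other, with the gap visible in between. Observation may end before week 16. If healing is the reason, which the documents do not say, the early healer may have a last-visit form and nothing after it. A model on a fixed 4-week grid would then estimate that patient's later scores from patients still under treatment. This stands and makes a bare repeated-measures model incomplete. It affects the planned week-16 t-test at least as much, because that test needs a value such a patient may not have.

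- **Importance.** This is one of seven secondary endpoints, with no sample size of its own, and the data remain analysable. That limits the weight of the point but does not remove it.

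**Conclusion.** The concern holds in a limited form. Read as written, the plan leaves the week 4, 8 and 12 readings of both questionnaires out of its stated test of the quality-of-life endpoint. The mismatch rests on the text alone and needs no assumption.

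Its size does need assumptions, because the documents give no quality-of-life variance, correlation or effect. The power figures show only that the choice of contrast can matter a great deal in either direction, depending on when the benefit appears. They do not show that the planned comparison is invalid or that the trial will miss an effect. The primary result is untouched. An inexpensive improvement is available and worth making before the data are analysed.

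**What to change.** In the Statistical analysis section:

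1. Analyse each questionnaire with one repeated-measures mixed model on all post-baseline readings (weeks 4, 8, 12 and 16), with baseline score as covariate and group-by-week terms.
2. Report the week-16 difference, as already planned, and add the average difference over weeks 4-16 from the same model, each with a 95% interval. Name in advance which one answers the endpoint.
3. State how a last-visit questionnaire completed before week 16 is assigned to a week, and how later readings are treated for a patient whose observation has ended. Add a sensitivity analysis, since missing readings may depend on healing.
4. State which EQ-5D visits build the QALYs.

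The cost is wording and a little analysis work. The contrasts use questionnaires already scheduled and need no extra patients; what exists after an early end depends on the rule in item 3. The drawbacks are a missing-at-random assumption, which the sensitivity analysis should probe, and the need to commit to one lead contrast.

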Specific questionnaires for recognition of costs (Economic section) will be administered to patients and their primary caregiver (if present) during the first visit, with the aim of identifying the resources absorbed by the patients (and their caregivers) treated in the two different approaches. The consumption of resources will be measured by gathering information about the quantification of direct health costs (visits, hospitalizations, emergency healthcare, medications etc...), direct non-health-related costs (informal medical assistance, transportation and accommodation costs for each visit etc...) and indirect costs (productivity loss for both the patient and the caregiver/s) and also by taking into account both the costs associated with the adherence to the treatment, taking the first visit as a reference parameter, and the costs related to complications and events associated with the ulcer that determined the need for treatments/ exams and/or medical evaluations. The Principal Investigator will be given also a questionnaire to determine the costs incurred by their facility for handling patients with leg ulcers.

The questionnaires meant to value customer satisfaction, complexity and helpfulness of EmoLED device will be administered to doctors and to healthcare personnel involved in the treatment at the end of the trial.

Image Acquisition

For the 16 weeks of the trial, during each visit a picture of the lesion will be taken, so that the process of healing can be valued also in a visual way. Each picture will be named with the patient code and the date of the visit. The quantitative analysis about the size of the lesions through the collected pictures will be performed at certain time points: at the beginning, in the middle and at the end of the treatment.

The image analysis is made through an appropriate analysis algorithm that measures the area of the lesion (mm²). The lesion must be fully and frontally framed to obtain an optimal analysis. The ruler with patient's ID code and date must appear in every picture. It is important that the ruler is placed straight and in-focus to have the scale reference. If there is a wide lesion that needs more than one picture it's advisable to

L.U.C.E. Study Protocol version 3.0 (24/02/2020)

locate several markers around the lesion and take photos of adjacent areas, including at least two visible markers of the previous picture, to have the complete image of the lesion through a sequential photo array.

Bias

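### Costs are tested on ranks, but the ICER in the same section needs the difference in mean cost, and no uncertainty is planned for that difference or for the ICER

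*Combined protocol and SAP*

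**What the plan says.** All of the planned cost analysis is in the Statistical analysis section.

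- The comparison of costs between groups, in both perspectives, "will be made using the non-parametric Mann-Whitney U test". The reason given is that cost distributions are usually skewed.
- The next sentence reads "Generalized linear regression models will be used to value the differences between the groups to eliminate any confounding factors". It names no outcome. It follows the cost sentence just as the linear regression sentence follows the t-tests, so adjusted mean cost is its most natural subject.
- Cost-effectiveness "in the time frame of the study (16 weeks) will be valued by calculating the incremental cost-effectiveness ratio (ICER"), expressed as incremental cost per QALY. Longer horizons are to be extrapolated with decision models.

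Neither this section nor any other states a confidence interval, bootstrap, acceptability curve or net-benefit analysis for the cost difference or the ICER.

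Two other places bear on the shape of the costs. Measurable parameters plans visits at two rates: in Group 1, "32 treatments are planned during 16 weeks, 2 per week"; in Group 2, "16 treatments are planned during 16 weeks, 1 per week". These are maxima, because Objectives of the study says of the observation period that "it may end at the 16th week or earlier". The Data Collection Form section lists what is costed: "quantification of direct health costs (visits, hospitalizations, emergency healthcare, medications etc", and so on), and also "the costs related to complications and events associated with the ulcer".

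**The concern.** Mann-Whitney asks whether a patient in one arm tends to cost less than a patient in the other. It equates to a comparison of means only under a further assumption, such as a pure shift between two distributions of the same shape, and the plan states none. By standard definition the numerator of an ICER is the difference in arithmetic mean cost. Skewness is a reason for care in estimating that difference; it does not make a rank comparison an answer to the same question.

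This trial combines the two ingredients that let ranks and means part: a routine cost that differs between arms by design through the visit schedule, and occasional expensive events such as admissions and complications. Ranks register the routine saving, while a handful of events can dominate the mean. At stake is how the economic results are read. A small p-value on ranks could be taken as confirming the cost side of the ICER when the mean difference behind that ICER is too imprecise to show even its sign. The plan calls for nothing that would reveal this.

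**Working it through.** **No figure to reproduce.** The documents state no expected cost, variance, complication rate or power for the economic endpoints. What follows is an illustration, and every cost value in it is assumed.

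**Inputs**
- From the document: 80 patients randomized 1:1, so n = 40 per arm.
- Assumed: routine cost lognormal with mean 1 in Group 1 and 1 − s in Group 2, with s = 0.33, 0.20 or 0.10 and CV 25, 50 or 100%.
- Assumed: a complication with probability p = 0.05 in both arms, adding K = 3, 5 or 10 times the Group 1 routine mean.
- 20,000 simulated trials per scenario.

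**Step 1: the true difference.** The Group 1 mean cost is 1 + Kp and the true saving is s, so the relative saving is s/(1 + Kp).
- Largest: 0.33/(1 + 3 × 0.05) = 0.33/1.15 = 29%.
- Smallest: 0.10/(1 + 10 × 0.05) = 0.10/1.50 = 7%.

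**Step 2: how a mean can reverse while ranks do not.** About 40 × 0.05 = 2 complications are expected per arm. At K = 10, one extra event in Group 2 raises its mean by 10/40 = 0.25, which outweighs a routine saving of 0.20. At K = 3 one extra event adds 3/40 = 0.075, so three are needed (0.225). In the rank test one such event moves a single patient to the top of the ordering.

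**Step 3: how often the two disagree.** Percentage of trials in which Mann-Whitney has p < 0.05 with Group 2 cheaper, while the observed Group 2 mean is at least that of Group 1, at K = 3 / 5 / 10:

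| Routine saving | CV 25% | CV 50% | CV 100% |
|---|---|---|---|
| 33% | 1.7 / 8.8 / 22.3 | 0.7 / 5.5 / 18.1 | 0.1 / 0.6 / 4.0 |
| 20% | 6.1 / 16.4 / 31.5 | 0.2 / 2.0 / 6.7 | 0.0 / 0.2 / 1.0 |
| 10% | 2.0 / 4.5 / 9.1 | 0.0 / 0.3 / 1.2 | 0.0 / 0.0 / 0.3 |

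The range is 0-32%. With complications in 10% or 15% of both arms it is 0-31%; with 10% in Group 1 and 5% in Group 2 it is 0-11%.

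**Step 4: precision of the mean difference.** The variance is v1 = CV² + K²p(1 − p) in Group 1 and v2 = CV²(1 − s)² + K²p(1 − p) in Group 2. The half-width is about 1.99 × √((v1 + v2)/40), divided by 1 + Kp.
- Narrowest (CV 25%, K = 3, s = 0.33): v1 = 0.0625 + 0.4275 = 0.490 and v2 = 0.0281 + 0.4275 = 0.456. Then 1.99 × √(0.946/40) = 0.306, and 0.306/1.15 = 27%.
- Widest (CV 100%, K = 10, s = 0.10): v1 = 1 + 4.75 = 5.75 and v2 = 0.81 + 4.75 = 5.56. Then 1.99 × √(11.31/40) = 1.06, and 1.06/1.50 = 71%.

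The simulated average half-widths are 26% and 69%, with Welch coverage of 95-97%. In 26 of the 27 scenarios the half-width exceeds the true saving, so an interval that includes zero would be common.

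**The case against.** The strongest reply is that the plan already covers mean cost. A generalized linear model for cost models the mean and yields a standard error. Evaluating costs (secondary endpoint 4) is not stated to mean evaluating mean cost, and a rank test is a legitimate description of skewed data. The plan never says that Mann-Whitney supports the ICER. Much of this stands. A reader might infer that the plan has no mean-cost analysis at all, or that Mann-Whitney is invalid here; the text supports neither. Leaving family, link and covariates unnamed is missing detail and would not carry the point alone.

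A second reply is that the illustration does not show the rank test misleading anyone. That is also right. In every base-case scenario Group 2 is truly cheaper and Mann-Whitney points the right way; the disagreement comes from a noisy sample mean. A reader might go further and infer that the test would name the wrong arm as cheaper, or that the arms' cost tails differ. The documents give no cost distributions and no basis for either.

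What these replies leave untouched is that the only named cost test addresses a different quantity from the ICER numerator, and that the numerator and the ratio would be reported without stated uncertainty. The noise in the sample mean is the reason an interval is needed.

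**Conclusion.** The concern holds in a limited form. As written, the plan tests the rank ordering of costs, builds its cost-effectiveness result on mean costs, and provides no interval for the mean difference and no uncertainty for the ICER. Secondary endpoints 4 (costs) and 7 (cost-effectiveness) are affected; the primary endpoint and the sample size are not.

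The size cannot be derived from the documents. Frequent disagreement needs fairly uniform routine costs together with very expensive events; at a routine CV of 100% it is at most 4% in the base case. The firmer result is the imprecision, since wide intervals appear in every scenario examined. Real costs could fall outside the assumed ranges.

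**What to change.** For each perspective, in the Statistical analysis section:

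1. Make the main cost comparison the difference in arithmetic mean cost per patient over 16 weeks, with a Welch or bootstrap 95% CI. Keep Mann-Whitney as descriptive.
2. Identify the generalized linear model as the adjusted mean-cost analysis, and report its group difference on the cost scale.
3. Report the ICER with a joint bootstrap of the cost and QALY differences, shown as a cost-effectiveness plane with an acceptability curve or net benefit. A plain interval on the ratio is unsuitable, because it becomes unstable when the QALY difference is near zero.

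This takes SAP wording and a modest amount of analysis. It needs no cost data beyond what the 16-week ICER already requires. Whether those data will exist should be confirmed first: the Data Collection Form section places the cost questionnaires at the first visit and gives no timing for the costs of complications.

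The downsides are real. Intervals will be wide at 40 per arm. Significant cost results will be fewer: in the base case Welch is significant in 5-60% of trials and Mann-Whitney in 7-100%. The percentile bootstrap may under-cover (89-95% in 1,000 trials of 1,000 resamples, at K = 3 and 10). A gamma log-link Wald test rejected in about 7-10% of trials when the two cost distributions were identical, so the adjusted model should not be treated as exact either.
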